#### ***9.1.7.1 Daily Surveys***

The daily survey questions will be completed on the Empower app and include questions about non-scheduled anxiety medication use (e.g. benzodiazepine dose taken over the past 24 hours and day/time of last dose), anxiety severity over the past 24 hours, anxiety interference with daily life over the past 24 hours, and anxiety severity at the present time. For anxiety severity, the participant will be asked to rate it on a 100-point visual analog scale (VAS) [0="No anxiety at all" through 100="Severe Anxiety"]. For anxiety interference with daily life, the participant will be asked to rate it on a 100-point visual analog scale (VAS) [0="Not at all" through 100="Extreme"].

The app will guide the participant to complete the daily survey prior to self-administering the first treatment session of each calendar day. Immediately after the session, the participant will also be asked about anxiety severity at the present time and if a tingling sensation was felt on the skin at the site of stimulation application to confirm effective nerve stimulation.

#### ***9.1.7.2 Weekly Surveys***

The weekly surveys (BAI) will be completed on the Empower app. The app will guide the participant to complete the weekly survey prior to self-administering the first treatment session of each calendar week.

#### ***9.1.7.3 Surveys only at Visits 1 and 3***

Surveys conducted at Visits 1 and 3 (GAD-Q-IV, PHQ-9, PSQI, and SF-12) will be completed electronically or on paper. At Visit 3, the participant will also complete the following electronic or paper-based surveys: usability survey (SUS), rating of overall satisfaction with treatment (100-mm VAS), blinding assessment, and a Final Study Questionnaire that includes questions regarding feedback on device features, device comfort and tolerability, and marketing questions.

#### **9.1.8 Treatment Session**

[REDACTED]

[REDACTED]

[REDACTED]

**9.1.9 Treatment regimen reminders sent to participants via text message**

[REDACTED]

[REDACTED]

[REDACTED]

[figure not shown]
[REDACTED]

[REDACTED]

[figure not shown]
[REDACTED]

[REDACTED]

[REDACTED]

#### **9.1.10 Contact with participants who are not adhering to the treatment regimen**

the clinical site research staff will contact the participant and request that they comply with the study procedures.

#### **9.1.11 Adverse Events**

Information regarding occurrence of AEs and serious AEs (SAEs) will be captured throughout the study. Duration (start and stop dates), severity/grade, outcome, treatment and relation to study device and procedures will be recorded on the case report form (CRF).

If the participant's skin becomes too irritated to comfortably carry out the treatment sessions, the participant will be instructed to refrain from administering a treatment session until the skin is no longer irritated.

#### **9.1.12 Suicidality Evaluation**

The C-SSRS-R will be used to evaluate suicidality risk at each clinic visit. If a participant exhibits suicidality or is determined to be at risk for harm to self/others by the clinician, the participant will be referred to his/her current mental health provider or primary care provider and will be provided information on community resources. In the event of acute suicidality, as confirmed on the C-SSRS-R with a "Yes" response to question 4 or question 5, or to question 6 in the past 3 months, the participant will be referred to the emergency department or psychiatric emergency services and withdrawn from the study.

#### **9.1.13 Participant Compensation**

Participants will be compensated a nominal amount for their time and expenses associated with the study. Each participant will be compensated \$100 for the screening/enrollment visit (Visit 1), \$100 each for the remaining two visits (Visits 2 and 3), and a bonus of \$25 for returning the study equipment (Empower controller and smartphone), for a total compensation of up to \$325 per participant. Compensation at Visits 2 and 3 includes compensation for the time and effort of conducting twice daily treatment sessions at home during the study.

## 9.2 Clinical Laboratory Measurements

### 9.2.1 Pregnancy Test

A urine pregnancy test will be obtained from female participants at the screening visit.

## 10 EVALUATIONS BY VISIT

### 10.1 Visit 1 (Day 1)

1. Review the study with the participant and obtain written informed consent and HIPAA authorization and assent
2. Assign the participant a unique screening number
3. Record demographics data
4. Record medical history
5. Record concomitant medications
6. Perform an abbreviated physical examination
7. Perform an abbreviated psychiatric examination, including M.I.N.I. and C-SSRS-R
8. Collect urine sample and perform a urine pregnancy test, if applicable
9. Perform clinician-administered assessments (HAM-A and HAM-D) and participant-reported survey (PCL-5)
10. Final review of eligibility
11. Complete self-report surveys (GAD-Q-IV, PHQ-9, PSQI, SF-12)
12. Randomize participant
13. Train participant on Empower device, smartphone, and app.
14. Self-administer a treatment session and complete app-based surveys (BAI, medication use, anxiety severity and interference, skin tingling)
15. Record adverse events, if applicable
16. Schedule participant for Visit 2 in 14 days

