The study will include three visits (all visits can be conducted by secure video call if the COVID-19 pandemic prevents in-person visits and Visit 2 can be conducted by phone):

- 1) Enrollment clinic visit (Day 1),
- 2) Mid-study clinic visit or phone/video call (Day 15 ± 7 days), and
- 3) Study completion clinic visit (Day 43 ± 7 days).

At Visit 1 (enrollment), the participant will first provide informed consent and be screened (screening includes clinician-administered M.I.N.I., C-SSRS-R, HAM-A, and HAM-D and participant-reported PCL-5). The warnings and contraindications as noted in the Instructions for Use (IFU) will also be discussed with the participant. If the participant meets all enrollment criteria, the participant will complete surveys (GAD-Q-IV, PHQ-9, PSQI, and SF-12). The participant will then be randomized to the active or sham treatment [REDACTED] and trained on device and app use, which includes training on how to self-administer a treatment session with the Empower Neuromodulation System. If the subject is randomized to the active treatment group [REDACTED]

[REDACTED] The participant will then self-administer a treatment session and answer all pre- and post-treatment session survey questions on the Empower app. During this initial treatment session, the participant will, under investigator supervision, adjust the stimulation intensity to a perceptible, yet tolerable level. After the session is completed, the clinical research staff will ask the participant about potential adverse events (AEs) via open-ended questioning. The participant will then be given an Empower system, supplies (skin electrodes, batteries, chargers), and the IFU to take home with him/her for self-administering treatment sessions at home.

At Visit 2 (mid-study visit), the participant will be asked about potential AEs via open-ended questioning, and the participant will be assessed for suicidality via the C-SSRS-R. The participant will also complete the blinding assessment. This visit may be conducted by phone.

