#### 15.4 Analysis of Secondary Endpoints

Secondary endpoints will be analyzed via the methods described below. Unless otherwise noted, for daily and weekly metrics, we will use a random-intercept linear mixed model with restricted maximum likelihood to compare results between the active and sham treatment groups. As a secondary analysis for each of these endpoints, we will evaluate the correlations for duration since last benzodiazepine dose and dose amount vs. the endpoint. If this relationship is significant for an endpoint, we will include time since last dose in our statistical analysis.

Feasibility: Effective nerve stimulation: We will calculate effective nerve stimulation (treatment sessions that elicit skin tingling as a percentage of total treatment sessions) for each participant. We will also compare effective nerve stimulation between the active and sham treatment groups (t-test).

Acceptability: Overall satisfaction with treatment: We will compare overall satisfaction with treatment scores between the active and sham treatment groups (t-test).

Safety: We will tabulate AEs across all participants. This will include tabulating the number of participants for whom the event occurred, the rate of occurrence, and the severity and relationship to the study device.

Effectiveness: Change in HAM-A score: We will compare the change in HAM-A score between the active and sham treatment groups (t-test).

Effectiveness: Change in GAD-Q-IV score: We will compare the change in GAD-Q-IV score between the active and sham treatment groups (t-test).

Effectiveness: Change in BAI score: We will compare the change in BAI score between the active and sham treatment groups (mixed models).

Effectiveness: Change in daily anxiety severity self-report: We will compare the change in daily anxiety severity scores between the active and sham treatment groups (mixed models).

Effectiveness: Change in daily anxiety interference self-report: We will compare the change in daily anxiety interference scores between the active and sham treatment groups (mixed models).

Effectiveness: Change in anxiety severity self-report as an immediate result of treatment: We will compare the short-term effect of Empower treatment on anxiety severity score (% change for post-treatment score vs. pre-treatment score) (repeated measures ANOVA with Tukey correction, active vs. sham treatment group).

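### The first BAI, daily anxiety severity and daily interference reports are collected after randomisation, while every other baseline scale precedes it

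*Combined protocol and SAP*

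**What the plan says.** Section 10.1 lists the Visit 1 procedures as numbered steps. HAM-A, HAM-D and PCL-5 are step 9. Step 11 is "Complete self-report surveys (GAD-Q-IV, PHQ-9, PSQI, SF-12". Step 12 is "Randomize participant", step 13 is "Train participant on Empower device, smartphone, and app", and step 14 is "Self-administer a treatment session and complete app-based surveys (BAI, medication use, anxiety severity and interference, skin tingling".

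The narrative in Section 4.4 follows the same order. After randomisation and training, and before the first session, it has a sentence beginning "If the subject is randomized to the active treatment group"; the rest is redacted. Section 9.1.4 also has site staff take a measurement, redacted, that the visible text ties to participants randomised to active treatment.

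Two sections set the order of survey and stimulation. Section 9.1.7.1: "The app will guide the participant to complete the daily survey prior to self-administering the first treatment session of each calendar day". Section 9.1.7.2 has the app guide the "participant to complete the weekly survey prior to self-administering the first treatment session of each calendar week". Section 9.1.7.1 words the medication, severity and interference items over the preceding 24 hours and has a separate item on anxiety at the present time.

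For the BAI, Section 15.4 says: "We will compare the change in BAI score between the active and sham treatment groups (mixed models". Daily severity and daily interference are treated the same way. None of the three entries defines baseline.

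**The concern.** A value recorded before allocation can differ between arms only by chance. A value recorded after allocation has no such protection. If training or arm-specific handling alters how participants answer, the difference enters the reference value and, through it, the estimated change. The three measures concerned are subjective self-reports, and the steps that come between differ by arm, at least in part.

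Blinding is also one of the things this pilot is testing. Section 5.1 says that finding a suitable sham is critical before a pivotal study, and the blinding index is a secondary endpoint. A baseline for the anxiety endpoints should not depend on how well the sham conceals allocation.

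The wording adds a second, smaller problem. Step 14 names the session before the surveys, and Section 9.1.7 describes surveys as done at the time of treatment. Staff who work literally from the Section 10.1 list could take the first BAI and daily items after stimulation, contrary to Sections 9.1.7.1 and 9.1.7.2.

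**Working it through.** The plan gives no figure that depends on this order. The check sets the sections side by side and then shows how a Day 1 shift would carry into the contrast.

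**1. Order relative to randomisation.** Before step 12: HAM-A, HAM-D, PCL-5 (step 9); GAD-Q-IV, PHQ-9, PSQI, SF-12 (step 11). After step 12: BAI, daily severity, daily interference and the daily medication question (step 14). Appendix 1 schedules the app surveys at Visit 1 and shows nothing earlier. Its rows are not in time order: it lists the PCL-5, which is needed for eligibility, below randomisation. Section 10.1 therefore governs the sequence.

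**2. Order relative to stimulation.** By Sections 9.1.7.1 and 9.1.7.2 the first daily survey and first BAI precede the first session, so they are post-randomisation but pre-stimulation.

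**3. Analyses that use the Day 1 value.** Section 15.4 analyses change in BAI, daily severity (read here as the 24-hour item) and daily interference. That makes three. Medication use is an average weekly benzodiazepine level on study with no Day 1 reference, and concomitant medications are recorded at step 5, before randomisation.

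**4. How much of a shift reaches the contrast.** Let one arm's Day 1 mean be shifted by δ, with no shift at later times. Section 15.4 specifies a random-intercept mixed model for daily and weekly measures but does not say how Day 1 enters. Possible cases:

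- *Simple change from Day 1:* the contrast moves by δ. A 5-point VAS shift gives 5 points.
- *Linear group-by-time trend, complete daily data, days 1 to 43 (assumed):* the slope difference moves by δ(t₁ − t̄)/Sxx. Here t̄ = 22, t₁ − t̄ = −21 and Sxx = 43(43² − 1)/12 = 6622. Over 42 days the size is δ × 42 × 21/6622 = 0.133δ. A 5-point shift gives 0.67 points.
- *The same model on seven weekly BAI values, weeks 0 to 6 (assumed):* Sxx = 7(7² − 1)/12 = 28, and the size is δ × 6 × 3/28 = 0.64δ.
- *Day 1 as a covariate:* the fraction is the regression coefficient on Day 1, which the documents do not give.

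**5. Scale, for illustration only.** Take 15 per arm (Section 15.5), a simple change score, a two-sample t-test at two-sided 0.05 (assumed; the plan states no alpha), no true effect, and a shift of b standard deviations of the change score. The noncentrality is b/√(2/15) on 28 degrees of freedom.

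| b (SD) | Noncentrality | False-positive rate |
|---|---|---|
| 0 | 0 | 0.050 |
| 0.1 | 0.27 | 0.058 |
| 0.2 | 0.55 | 0.083 |
| 0.3 | 0.82 | 0.125 |
| 0.5 | 1.37 | 0.262 |

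A normal approximation gives 0.059, 0.085, 0.130 and 0.278 for the last four rows. The documents give no value for b. The rates assume that the whole shift reaches the contrast, so they would be lower under the trend models in step 4.

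**The case against.** The strongest reply is that the plan already contains most of the protection. The surveys come before any stimulation, Section 4.4 says participants are blinded, and a question about the past 24 hours covers a period almost wholly before allocation. That stands, and it rules out a treatment effect in the baseline. It does not rule out a change in how the question is answered. The 24-hour argument also covers only the daily items, because the protocol states no recall period for the BAI.

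Four stronger readings are tempting, and the documents do not support them.

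- A reader might count medication use as a fourth affected endpoint. It is a level comparison with no Day 1 reference to disturb.
- A reader might infer that staff who know the allocation are with the participant when the surveys are answered. No section says so. The investigator supervision in Section 4.4 concerns adjusting the intensity during the session.
- A reader might infer that the arm-specific step reveals allocation or raises anxiety. Its content is redacted, a sham counterpart may sit in the redacted text, and nothing visible shows either effect.
- A reader might take any shift to pass in full into the result. That holds for a simple change score but not in general for the mixed models in Section 15.4.

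It can also be said that these are secondary endpoints in a 30-person pilot, and that adherence, SUS and all the clinician-rated and visit-based scales are untouched. That is correct and sets the weight of the point.

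**Conclusion.** The point holds in a limited form. Three change analyses (BAI, daily severity, daily interference) rest on first values taken after randomisation, training and a step described for the active arm, and Section 15.4 does not define their baseline. The exposure is to reporting or expectation bias only. It is probably small, and its size cannot be estimated from the documents. The share reaching the contrast runs from about 13% (linear trend, complete daily data) through about 64% (linear trend, seven weekly BAI values) to all of it (simple change score). Those shares assume that the shift affects Day 1 alone and that the data are complete. This is an inexpensive improvement to secondary endpoints and does not threaten the trial's primary aims.

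**What to change.** In Section 10.1, move the first BAI and the 24-hour anxiety severity and interference items to step 11, before randomisation. Staff-assisted entry on the app is preferable, so that the mode matches later reports. Leave the present-time anxiety ratings before and after the session, and the tingling question, at step 14, and reword that step so that the pre-session rating clearly comes first, as Section 9.1.7.1 requires. Adjust Sections 4.4 and 9.1.7 and the Synopsis to match. In Section 15.4, state that the pre-randomisation values are the baseline for the three change analyses, and say how baseline enters each mixed model.

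The cost is a small change to the Visit 1 app flow: brief help with the app before allocation, and a setting so that the moved items are not asked again on Day 1. If paper is used instead, baseline and later reports would differ in mode, which is why app entry is preferred. No extra visit, instrument or participant is needed, and Section 9.1.7 already provides for daily and weekly surveys to be completed at clinic visits.

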### 10.2 Visit 2 (Day 15 ± 7)

1. Complete blinding assessment
2. Record adverse events, if applicable
3. Perform assessment of suicidality (C-SSRS-R)
4. Schedule participant for Visit 3 in 28 days

### 10.3 Visit 3 (Day 43 ± 7)

1. Perform clinician-administered assessments (C-SSRS-R, HAM-A, HAM-D)
2. Complete self-report surveys (PCL-5, GAD-Q-IV, PHQ-9, PSQI, SF-12)
3. Record adverse events, if applicable
4. Complete blinding assessment, usability survey, and Study Completion Questionnaire
5. Return of all device and study materials
6. Participant reimbursement

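### Section 10 lists the treatment guess before adverse-event questioning at Visit 2 and before the co-primary SUS at Visit 3 and Early Withdrawal; other sections order these differently and none fixes the sequence

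*Combined protocol and SAP*

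**What the plan says.** **Visit 2.** Section 10.2 opens its numbered list with "Complete blinding assessment". AE recording is step 2 and the C-SSRS-R is step 3. Section 4.4 runs the other way: at this visit "the participant will be asked about potential AEs via open-ended questioning, and the participant will be assessed for suicidality via the C-SSRS-R", and only then "The participant will also complete the blinding assessment. This visit may be conducted by phone". The synopsis has the same order as 4.4.

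**Visit 3 and Early Withdrawal.** Step 4 of Section 10.3 is "Complete blinding assessment, usability survey, and Study Completion Questionnaire", and Section 10.4 repeats it for Early Withdrawal. The clinician ratings, the self-report surveys and AE recording ("Record adverse events, if applicable") are steps 1 to 3. Section 4.4, the synopsis and Appendix 1 also name blinding before usability at Visit 3. Sections 9.1.7 and 9.1.7.3 list the instruments as "usability survey (SUS), rating of overall satisfaction with treatment (100-mm VAS), blinding assessment", followed by the final questionnaire.

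**Role of the outcomes.** Section 5.1 makes acceptability, measured by SUS, a co-primary endpoint and ties its evaluation to finding a suitable sham for a pivotal study. Section 15.3 compares SUS between arms by t-test and compares each arm with benchmarks of 68 and 80. Section 5.3 makes device-related AEs a safety evaluation.

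**The concern.** SUS ratings and answers to open-ended AE questions are subjective. A participant who has just declared a belief that the device was sham may score its usability lower or leave out minor sensations. One who has just declared it active may do the reverse.

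Two comparisons are exposed. If guesses split differently by arm, which is what the planned blinding index examines, part of any active-sham difference in SUS or in Visit 2 AEs could come from the questioning rather than the device. Even if guesses split equally, each arm's SUS mean could shift relative to the 68 and 80 benchmarks.

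Visit 2 may be held by phone, so the guess might be spoken to the person who then records AEs. The documents do not say who takes the guess, so this is a possible route only.

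Because the sections disagree, the order could also vary between participants.

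**Working it through.** No sample size, power or effect figure enters this point. The check sets the sections side by side.

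| Source | Visit 2 | Visit 3 |
|---|---|---|
| 10.2 | guess (step 1), AEs (2), C-SSRS-R (3) | n/a |
| 10.3, and 10.4 for Early Withdrawal | n/a | clinician ratings (1), self-report surveys (2), AEs (3), then guess, SUS and questionnaire within step 4 |
| 4.4 and synopsis | AEs, C-SSRS-R, guess | guess, SUS, questionnaire |
| 9.1.7 and 9.1.7.3 | no order for AE questioning | SUS, satisfaction VAS, guess, final questionnaire |
| Appendix 1 (row order) | C-SSRS-R, AEs, guess | AEs, guess, usability and questionnaire |

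1. *Visit 2.* Section 10.2 stands alone. Section 4.4, the synopsis and the row order of Appendix 1 all put AEs and C-SSRS-R before the guess. The steps in 10.2 are numbered separately, so the difference does not depend on word order within a line.
2. *Visit 3.* Sections 10.3, 10.4, 4.4, the synopsis and Appendix 1 agree in naming the guess before SUS. Only 9.1.7 and 9.1.7.3 differ. In 10.3 and 10.4 the three instruments share one numbered step, so the order there is word order only.
3. *Would a site read Section 10 as a sequence?* Nothing says it must. But the Visit 1 list in 10.1 is plainly chronological: consent, eligibility review, surveys, randomization, training, treatment session, AE recording. Reading 10.2 to 10.4 the same way is natural.
4. *Which outcomes are exposed to a same-visit guess?* At Visit 2, open-ended AE reports and the C-SSRS-R. At Visit 3, SUS and the completion questionnaire. HAM-A, HAM-D, the self-report surveys and Visit 3 AEs are listed before the guess. The satisfaction VAS is not named in 10.3, and where it appears beside the guess (9.1.7, 9.1.7.3) it comes first.
5. *What would reordering leave in place?* The Visit 2 guess at Day 15 precedes the Visit 3 SUS at Day 43: 43 − 15 = 28 days nominally. With both windows at ±7 days, the gap runs from 36 − 22 = 14 to 50 − 8 = 42 days. Changing the order within each visit does not alter this.

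**The case against.** The strongest reply is that these are lists of what to do, not instructions on when. At Visit 3 the argument rests on word order inside one line, and two unordered lists that differ do not contradict each other. Appendix 1 shows that position need not mean timing: its randomization row sits above the self-report surveys, while 10.1 puts the surveys (step 11) before randomization (step 12). This stands as a limit on the claim, since the protocol does not mandate a guess before SUS. It also confirms that the order is unspecified, and it carries less weight against 10.2, where the steps are separately numbered.

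A second reply is that moving the guess last has its own cost. Questions about comfort, tolerability and AEs could prompt recollections that differ by arm and so shape the guess, and the blinding index is itself a secondary endpoint. The possibility is fair, so the choice is a design judgement. With SUS a co-primary endpoint and the guess a secondary one, the balance favours protecting SUS.

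A third reply is that participants may already hold a belief about allocation, which would colour SUS in any order, and that AEs are captured throughout the study and asked about again at Visit 3. Both are correct. They limit what the order of questions can add, but they do not make the order irrelevant.

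**Conclusion.** The point holds as a minor, inexpensive correction. The sections differ on where the guess falls, clearly at Visit 2 and by word order at Visit 3, and none fixes it. A site following Section 10 could plausibly take the guess immediately before subjective outcomes, including a co-primary one. This rests on two assumptions: that sites read Section 10 as a sequence, and that stating a guess can influence the answers that follow. The documents offer no data on the second, so no size can be given.

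A reader might infer more than the documents support:

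- That Section 4.4 contradicts Section 10 at both visits. It differs only at Visit 2 and agrees with 10.3 at Visit 3; 9.1.7 and 9.1.7.3 differ only at Visit 3.
- That satisfaction, HAM-A, HAM-D or Visit 3 AEs follow that visit's guess. No section lists them so.
- That a particular number of SUS points is at risk. Any such figure would need guess rates and a priming effect that the documents do not give.
- That reordering would remove the influence altogether. It removes same-visit priming only; the Visit 2 guess remains, nominally 28 days before SUS.

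**What to change.** State one explicit order of administration:

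- Visit 2 (10.2): AE recording and C-SSRS-R, then the blinding assessment as the last assessment.
- Visit 3 (10.3) and Early Withdrawal (10.4): SUS, satisfaction VAS and the Study Completion Questionnaire as separately numbered steps, then the blinding assessment as the last participant questionnaire. Naming the satisfaction VAS here also settles its position.

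Align the synopsis, 4.4, 9.1.7, 9.1.7.3 and Appendix 1, and say that the listed order is the order of administration. Sections 9.1.7 and 9.1.7.3 also need a small change, because they now place the guess before the final questionnaire.

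The cost is an edit to existing steps, with no added visit, instrument, staff time or data.
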